social connection (Maner, DeWall, Baumeister, & Schaller, 2007). This “cautious interest” makes sense considering that recently rejected people must balance their need for social connection against the risk of further rejection (Finkel & Baumeister, 2018). Thus, borrowing from DeWall et al. (Dewall, Maner, & Rouby, 2009), we focused on early-stage perceptual processes that are thought to maximize opportunities for social connection. Specifically, DeWall and colleagues showed that recently rejected (vs. control) participants oriented more quickly to faces signalling acceptance (in the form of a smile), but not disapproval. Similarly, we hypothesized that naltrexone (vs. placebo) would result in heightened social need manifested as increased attentional bias to smiling faces.

To test these hypotheses, we administered naltrexone and placebo on two occasions, approximately one week apart, and then assessed self-esteem and attentional bias to accepting (vs. neutral and rejecting) faces. Given our focus on changes in self-esteem, we elected to use a within-subjects design because it allows us to control for individual differences in trait self-esteem across drug conditions; moreover, a within-subjects design offers considerably greater statistical power, given the same number of participants, than does a between-subjects design.

Study Objectives

This study examined the effects of endogenous opioids on self-esteem and attentional bias toward social cues. This was accomplished by temporarily blocking endogenous opioid activity with the administration of an opioid receptor antagonist.

Study Design and Methods

All research procedures were approved by the McGill University Medical Institutional Review Board (protocol #A02-B12-11B). The study used a randomized, within-subjects, placebo-controlled design in which participants received 50 mg oral naltrexone and matching

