To test our hypotheses, we conducted a series of repeated measures analyses of variance (ANOVA) with drug condition (naltrexone or placebo) as the within-subjects factor, and self-esteem and VPT scores as the outcome measures; separate analyses were conducted for acceptance bias, rejection bias, and neutral-neutral trial RTs. To ensure that changes in the variables of interest were a function of the drug and not order of drug administration or the tasks participants completed prior to ours, we included order (naltrexone vs. placebo on Day 1), study participation (music pleasure vs. music cognition), and the interaction between these two variables as between-subjects factors in our statistical analyses. For full transparency, we also provide results without these control variables included in the model.

Results

Self-Esteem

The repeated measures ANOVA revealed a significant effect of drug on self-esteem, $F(1, 22)=5.18, p=.033, \eta^2=0.19$). As seen in *Figure 1*, mean self-esteem scores were lower on the naltrexone day ($M=3.27, SE=0.07$) compared to the placebo day ($M=3.39, SE=0.09$).¹ There were no effects of drug administration order or prior study on self-esteem, nor were there any significant interactions between these variables and drug condition (all $ps > .050$). Of note, we also observed a significant drug order by prior study interaction, $F(1, 22)=5.60, p=.027$ on self-

¹ When the order of drug administration and prior study variables were removed from analysis, the test statistics for the drug effect were as follows: $F(1, 25)=6.45, p=.018, \eta^2=0.20$.

esteem; however, none of the contrasts were significant (all $ps > .050$), rendering this effect uninterpretable.

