As an exploratory analysis, we also examined the effect of naltrexone vs. placebo on the self-liking and self-competence subscales of our self-esteem measure separately (Tafarodi & Milne, 2002). Results showed that participants reported significantly lower self-liking on the naltrexone day, $M=3.05$, $SE=0.10$, relative to the placebo day, $M=3.21$, $SE=0.11$, $F(1, 22)=6.54$, $p=.018$, $\eta^2=0.23$, whereas there was no effect of naltrexone on the self-competence subscale, $F(1, 22)=1.56$, $p=.225$, $\eta^2=0.07$.² Results also showed the same drug order by prior study interaction that was observed for overall self-esteem on self-liking ($F(1, 22)=8.72$, $p=.007$), but not self-competence ($p > .050$); other than this one interaction, there were no significant effects of drug administration order or prior study, nor were there any significant interactions between these variables and drug condition on either self-liking or self-competence component scales (all $ps > .050$).

Acceptance Bias

The repeated measures ANOVA yielded a significant effect of drug on acceptance bias, $F(1, 20)=4.42$, $p=.048$, $\eta^2=0.18$. As illustrated in *Figure 2*, acceptance bias scores were significantly higher following naltrexone ($M=15.03$, $SE=7.23$) vs. placebo ($M=-6.52$, $SE=6.35$), indicating that participants showed greater attention to accepting faces following naltrexone (vs. placebo) administration.³ There were no main or interaction effects of drug administration order or prior study on acceptance bias (all $ps > .050$).

² When the order of drug administration and prior study variables were removed from analysis, the test statistics for the drug effect were as follows: (1) self-liking: $F(1, 25)=7.58$, $p=.011$, $\eta^2=0.23$; (2) self-competence: $F(1, 25)=1.23$, $p=.278$, $\eta^2=0.05$.

³ When the order of drug administration and prior study variables were removed from analysis, the test statistics for the drug effect were as follows: $F(1, 23)=2.29$, $p=.143$, $\eta^2=0.09$.

Rejection Bias

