In contrast to the findings for acceptance bias, there were no significant effects of drug on rejection bias scores, $F(1, 20)=1.33, p=.262, \eta^2=.06$.⁴ In fact, the pattern of results was in the opposite direction from the acceptance bias score with nominally (but not significantly) less attention to rejecting faces following naltrexone ($M = -6.02, SE = 4.32$) vs. placebo ($M = 1.35, SE = 5.12$). There were no main or interaction effects of drug administration order or study on rejection bias (all $ps >.050$).

Neutral-Neutral Trial RT

The repeated measures ANOVA showed no significant effect of drug on neutral-neutral trial RTs, $F(1, 20) = 0.34, p=.566, \eta^2=0.02$, although there was a significant drug by drug order effect, $F(1, 20) = 11.84, p = 0.003$: for participants who received naltrexone on Day 1, reaction times were greater in the naltrexone vs. placebo condition, $M_{diff}=35.90, F(1, 20)=12.69, p=.002$, whereas there was no difference between drug condition for participants who received placebo on Day 1, $M_{diff}=-25.48, F(1, 20)=3.00, p=.099$. Importantly, even though there may have been a slowing down of RTs in general (at least for those who received naltrexone on Day 1), this would not explain the primary effect of interest—i.e., faster RTs to accepting faces following naltrexone—in fact, this general slowing down would, if anything, work against this effect.

⁴ When the order of drug administration and prior study variables were removed from analysis, the test statistics for the drug effect were as follows: $F(1, 23)=0.80, p=.380, \eta^2=0.03$.

References

- Dandeneau, S. D., Baldwin, M. W., Baccus, J. R., Sakellaropoulou, M., & Pruessner, J. C. (2007). Cutting stress off at the pass: Reducing vigilance and responsiveness to social threat by manipulating attention. *Journal of Personality and Social Psychology*, *93*(4), 651–666. <http://doi.org/10.1037/0022-3514.93.4.651>
- Denissen, J. J. A., Penke, L., Schmitt, D. P., & van Aken, M. A. G. (2008). Self-esteem reactions to social interactions: Evidence for sociometer mechanisms across days, people, and nations. *Journal of Personality and Social Psychology*, *95*(1), 181–196. <http://doi.org/10.1037/0022-3514.95.1.181>
- Dewall, C. N., Maner, J. K., & Rouby, D. A. (2009). Social exclusion and early-stage interpersonal perception: Selective attention to signs of acceptance. *Journal of Personality and Social Psychology*, *96*(4), 729–741. <http://doi.org/10.1037/a0014634>

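### The contrasts between accepting and rejecting faces, and between self-liking and self-competence, rest on separate ANOVAs; neither difference is tested, with or without the control variables

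*Combined protocol and SAP*

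**What the plan says.** The Statistical Analyses section describes repeated measures ANOVAs "with drug condition (naltrexone or placebo) as the within-subjects factor" and adds that "separate analyses were conducted for acceptance bias, rejection bias, and neutral-neutral trial RTs". Order, prior study and their interaction enter as between-subjects factors. The section also commits to a second version: "For full transparency, we also provide results without these control variables included in the model". The exploratory subscale analysis, under Self-Esteem in the Results, likewise treats self-liking and self-competence one at a time.

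Two comparisons follow in the Results.

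- Rejection Bias: "In contrast to the findings for acceptance bias, there were no significant effects of drug on rejection bias scores". The next sentence says the pattern ran in the opposite direction.
- Self-Esteem: self-liking fell on the naltrexone day, "whereas there was no effect of naltrexone on the self-competence subscale" (p=.225).

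The Background motivates the task with an earlier study in which rejected "participants oriented more quickly to faces signalling acceptance (in the form of a smile), but not disapproval". The Background and the Study Design section both describe the assessment as a comparison of accepting with rejecting faces.

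The only interactions reported involve order or prior study. Footnotes 2 to 4 give just the drug effect within each outcome.

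**The concern.** One significant and one non-significant result do not show that two effects differ. That needs a test of the difference itself: the drug-by-face-type or drug-by-subscale interaction, which is the same as a paired comparison of the two drug differences.

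What is at stake is the selective reading: that naltrexone shifts attention to accepting but not rejecting faces, and lowers self-liking but not self-competence. For faces, this reading parallels the result of the social-exclusion study cited in the Background. For the subscales it is exploratory. The hypothesis as written concerns smiling faces only, and the acceptance-bias ANOVA tests it.

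The version without control variables matters because acceptance bias itself moves from p=.048 to p=.143 there. The answer on selectivity may depend on the same choice.

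**Working it through.** **1. The printed tests reproduce.** Upper tail of F on 1 and the stated error df:

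| Outcome | With controls | p | Without controls | p |
|---|---|---|---|---|
| Acceptance | F(1,20)=4.42 | .048 | F(1,23)=2.29 | .144 (printed .143; agrees within rounding of F) |
| Rejection | F(1,20)=1.33 | .262 | F(1,23)=0.80 | .380 |
| Self-liking | F(1,22)=6.54 | .018 | F(1,25)=7.58 | .011 |
| Self-competence | F(1,22)=1.56 | .225 | F(1,25)=1.23 | .278 |

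**2. Face type, adjusted model.** This assumes that the printed means are the ones the adjusted F tests.

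- Acceptance: 15.03 - (-6.52) = 21.55; SE = 21.55/√4.42 = 10.25.
- Rejection: -6.02 - 1.35 = -7.37; SE = 7.37/√1.33 = 6.39.
- Difference of drug effects: 21.55 - (-7.37) = 28.92 ms.
- SE of the difference = √(10.25² + 6.39² - 2r·10.25·6.39), where r is the unreported correlation between the two drug differences.

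| r | SE | F(1,20) | p | 95% CI (ms) |
|---|---|---|---|---|
| -.5 | 14.54 | 3.96 | .061 | -1.41 to 59.25 |
| 0 | 12.08 | 5.73 | .027 | 3.72 to 54.12 |
| .5 | 8.97 | 10.40 | .004 | 10.22 to 47.62 |

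p falls below .05 for r above about -.35.

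**3. Face type, without control variables.** The printed mean difference cannot be reused: 21.55/√2.29 = 14.24, which exceeds the largest SE that the printed condition SEs allow (7.23 + 6.35 = 13.58). A bound needs no means. With s1 and s2 the unknown SEs of the two drug differences, and effects in opposite directions,

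F = (√2.29·s1 + √0.80·s2)² / (s1² + s2² - 2r·s1·s2).

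Its maximum over all s1 and s2 is (2.29 + 0.80 + 2r√(2.29·0.80)) / (1 - r²). A numerical search over s2/s1 gives the same values.

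| r | Largest possible F(1,23) | Smallest possible p |
|---|---|---|
| -.5 | 2.32 | .142 |
| 0 | 3.09 | .092 |
| .25 | 4.02 | .057 |
| .5 | 5.92 | .023 |

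The critical value 4.28 is reached at r=.298 (.296 to .301 allowing for rounding of the Fs). Opposite directions are the case most favourable to the text; if the two effects had the same direction, the cap would be 2.29 for r up to about .59.

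**4. Self-competence, from F alone.** With t(.975, 22)=2.074, the 95% CI as a multiple of the observed change is 1 ± 2.074/√1.56 = 1 ± 1.66, that is -0.66 to 2.66. It includes zero, and also a change more than twice the one observed.

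**5. Subscale difference, adjusted model.** This assumes five items per subscale, a split the documents do not give.

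- Overall drop: 3.39 - 3.27 = .12. Self-liking drop: 3.21 - 3.05 = .16. Implied self-competence drop: 2(.12) - .16 = .08.
- SEs: self-liking .16/√6.54 = .0626; self-competence .08/√1.56 = .0641; overall .12/√5.18 = .0527.
- The overall score is then the mean of the two subscales, so the SE of the difference = √(2·.0626² + 2·.0641² - 4·.0527²) = .0701.
- Difference .16 - .08 = .08; F(1,22) = (.08/.0701)² = 1.30; p about .27.

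Letting the overall drop range over .11 to .13 and the self-liking drop over .15 to .17, to allow for rounding, gives p from .03 to .68.

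**The case against.** The best defence is that no selectivity conclusion is formally stated. The hypothesis concerns smiling faces, the wording on rejection bias is qualified as nominal and not significant, and the line about disapproval describes another study. In the adjusted model the face contrast probably survives: the two bias scores come from different trials, and nothing in the documents points to a strongly negative r. Without control variables neither face type is significant, so the text draws no contrast there, and the calculation is only an upper bound. The subscales are labelled exploratory, and their computed p rests on an assumed item split. Rewording alone might do.

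Much of this stands. The hypothesis test is untouched, the adjusted face contrast may hold, and the subscale difference is undetermined. Two things remain. First, the qualifier on rejection bias concerns the rejection effect, not the difference between effects, and the text does set the two results against each other; the self-competence sentence has no qualifier at all. Second, the documents themselves frame the assessment as accepting versus rejecting faces and promise results in both versions. Rewording would remove the overstatement but leave that comparison unanswered, although the data to answer it are in hand.

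**Conclusion.** The concern holds, within limits. Two contrasts are drawn that no reported analysis tests, in either version of the model. This should be corrected, but it does not undermine the test of the written hypothesis.

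- **Faces, adjusted:** the missing test may well favour the text. This rests on the printed means being those the adjusted F tests, and on r, which only the sponsor can compute.
- **Faces, without control variables:** significance is out of reach for r below about .30 and possible, not assured, above it. This uses only the two printed Fs. The two versions may therefore disagree.
- **Subscales:** unresolved. The figure of about .27 depends on an assumed item split and on means rounded to two decimals.
- **Self-competence:** the data are compatible with no change and with a change larger than the one observed, so the claim of no effect is not supported.

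**What to change.** Keep the acceptance-bias ANOVA as the test of the written hypothesis. Add text such as:

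> Post hoc, after the main results were known, we tested whether the drug effect differs by face type in a repeated measures ANOVA on bias scores, with drug and face type (accepting, rejecting) as within-subjects factors. We ran it with order, prior study and their interaction as between-subjects factors, and again without them. An exploratory post hoc model of the same form used drug and subscale (self-liking, self-competence), also with and without these terms.

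Report each interaction estimate with its 95% CI in both versions. For self-competence, state that the effect was not significant, and give the estimate and 95% CI. Drop the contrast wording wherever the interaction does not support it, and say so if the two versions disagree.

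The cost is two further models, each run twice, on existing data. With 24 and 26 participants the estimates will be imprecise, and the contrast wording may have to be softened.
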